7.2.9 Treatment Discontinuation

Odevixibat treatment may be discontinued based on the judgement of the treating physician, including in the event of any serious adverse events (SAEs), AEs, or Special Situations (see Section 9.1.3 for definition of Special Situations) deemed by the investigator to warrant treatment discontinuation. In the event of pregnancy, odevixibat treatment may be discontinued based on the judgement of the treating physician (Section 9.1.3.1).

Discontinuation of treatment due to **AEs** should be distinguished discontinuation/withdrawal from the study due to participant/parent decision or end of followup.

If AEs or their sequelae (any AE, based on the investigator's opinion, not only those assessed as related) persist after the date of odevixibat discontinuation the investigator must ensure that the participant receives appropriate medical follow-up and this should be properly documented in the participant's medical records.

All participants discontinuing odevixibat treatment will be followed up to 180 days after last odevixibat dose (unless consent is withdrawn) or until the end of data collection, whichever comes first.

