The majority of patients present with severe, intractable pruritus, which can be disabling. Attempts at managing pruritus are made by including ursodeoxycholic acid (UDCA), cholestyramine, rifampin, ondansetron, and/or naltrexone in the patient's treatment regimen; these agents are at best partially effective (Singh 2018). Biliary diversion surgery is occasionally used to treat intractable pruritus with some success (Emerick 2002; Mattei 2006). Treatment of persistent cholestasis and progressive liver cirrhosis is supportive and usually includes a choleretic agent. Kasai hepatoportoenterostomy has been attempted to increase biliary flow from the liver to the intestine, but unlike patients with biliary atresia, those with ALGS who undergo the procedure have a worse outcome (Sheflin-Findling 2012). Approximately 15% to 25% of patients with ALGS will require a liver transplant during childhood. For patients with ALGS there is a positive response to transplant with about 90% of patients showing improvement in liver parameters and some degree of catch-up growth. The 5-year survival post-transplant in this population is about 80% (Pawlowska 2010).

Odevixibat has minimal systemic exposure at therapeutic dose ranges, and the efficacy of odevixibat is driven by the intralumenal concentrations and not by systemic exposures. By inhibiting the IBAT with high selectivity and potency, odevixibat reduces the systemic accumulation of bile acids that result from cholestasis, relieves pruritus, and improves liver function. Because odevixibat targets the final common pathways of elevated serum bile acids and pruritus rather than the underlying specific genetic mutations, odevixibat is expected to provide clinical benefit. The clinical data collected to date support this expectation.

The efficacy of odevixibat in patients with ALGS was demonstrated in the Phase 3 study A4250-012 (ASSERT), a randomized, double-blind, placebo-controlled study. In this study,

PAGE 20 OF 76

odevixibat treatment resulted in statistically significant improvements in pruritus when compared with placebo.

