7.2.2 Exclusion Criteria

Participants will not be included in the registry-based study if:

- (1) Currently participating in a clinical trial with odevixibat.
- (2) Currently participating in any interventional clinical trial for ALGS.
- (3) Have any contraindication to odevixibat as per the locally approved label.
- (4) Had liver transplant before enrolment.

Individuals who do not meet the criteria for participation in this registry-based study (screen failure) or who withdraw their consent may be rescreened. Rescreened participants should be assigned a new participant number. The informed consent process is described in Section 7.13.

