7.2.4 Study Duration

The duration of the registry-based study is approximately 5 years. Participants will be followed for ≥ 2 years. Enrolment will close 3 years after the start of the study to ensure participants are followed for ≥ 2 years. Following enrolment, participants will continue to participate in the study until the time point of withdrawal of consent, for up to 180 days after last dose of odevixibat (in case of treatment discontinuation), death, the end of data collection, or the sponsor decides to discontinue the study.

Participant enrolment will start on the date that the investigational site has been activated.

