- ¹ The fat-soluble vitamin deficiency questionnaire will be included in the eCRF and completed by the investigator (Section 7.6.1).

PAGE 26 OF 76

7.2.7 *Study Visit(s)*

Visits will be done in accordance with routine clinical practice (Follow-up Visits are expected to occur at least every 6 months or more frequently, based on the investigator's judgement). Investigators are encouraged to contact the participants (e.g., text-based reminders or phone calls to caregivers) to ensure follow-up visits are attended and to facilitate rescheduling, if necessary.

The registry-based study will assess data collected at the Baseline Visit and Follow-up Visits.

The End of Study for participants will be the last Follow-up Visit as per routine clinical practice performed before the planned end of data collection (approximately 5 years after the start of data collection, see Section 4), withdrawal of consent, lost-to follow up, or 180 days after treatment discontinuation, whichever comes first.

7.2.7.1 *Baseline*

Investigators at participating sites will identify participants who fulfil the inclusion and none of the exclusion criteria. Signed informed consent should be obtained prior to enrolment based on local regulations, and once inclusion and exclusion criteria have been satisfied. If the participant is < 18 years old (or the legal age of consent in the jurisdiction in which the study is taking place), assent and parent or legally authorized representative consent will also be required.

For this registry-based study, the following variables will be captured from Baseline Visit records as available:

- Age, sex, weight, height, ALGS genetic variant, date of birth (MM/YYYY), and date
 of ALGS diagnosis
- General medical or surgical history
- Prior surgical procedures related to ALGS, including but not limited to prior biliary diversion surgery (date and type of surgery) and liver transplantation (date and donor information)
- Prior medications
 - Prior medications refer only to medications related to the treatment of ALGS, including but not limited to rifampicin, UDCA, and/or other IBAT inhibitors, taken up to 9 months prior to the first odevixibat dose
- Concomitant medications
 - Concomitant medications include ALGS and non-ALGS oriented treatments, including but not limited to rifampicin and UDCA
- Concomitant vitamin supplementation
- Odevixibat treatment dose and start date

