7.2.8 Study Discontinuation/Withdrawal

The participant can withdraw (or be withdrawn if the participant is a child upon legal representative's decision) from this registry-based study at any time. The date and primary reason for withdrawal should be recorded in the eCRF as well as if the participant stopped odevixibat or not.

For study results to remain unbiased, it is important that no data are modified; as a result, the data collected in clinical studies need to remain untouched for results to be trusted. Should the participant withdraw from the study, no further data will be collected; nevertheless, data collected up to the time of the withdrawal will be kept for analysis, safety, and integrity of study results.

PAGE 28 OF 76

The participant will be withdrawn from the registry-based study if:

- They enroll in any interventional clinical trial
- The participant is no longer receiving odevixibat and has completed the last follow-up visit up to 180 days after last dose of odevixibat (see Section 9.4 for follow-up of AEs and Section 9.1.3.1 for follow-up of pregnancies)

Note: Participants can remain in the registry-based study during odevixibat treatment interruptions.

Investigators may decide to stop their participant's participation in the study at any time without consequences on the normal participant follow-up.

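### The primary endpoints have no on-treatment limit, but all collection stops at most 180 days after the last odevixibat dose, so later diversions, transplants and deaths are never recorded

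*Protocol*

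**What the plan says.** **Endpoints.** Protocol Section 7.3.1.1 lists the incidence of diversion, transplant or death, then diversion-free, transplant-free and overall survival. All three survival times start at the first odevixibat treatment and end at the event. None is restricted to time on treatment. Section 7.7.2.1 summarises incidence descriptively and the survival endpoints by Kaplan-Meier at 6-month steps.

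**Collection.** Section 7.2.9: "All participants discontinuing odevixibat treatment will be followed up to 180 days after last odevixibat dose" (or to the end of data collection, if earlier). Section 7.2.7 and Table 1 footnote b make 180 days after discontinuation one of the events that end the study for a participant. Section 7.2.8 withdraws anyone who is off odevixibat and has had that last visit, and says that nothing is collected after withdrawal. I find no exception for vital status, transplant or diversion. The only follow-up that runs longer is for pregnancy (Section 9.1.3.1). Treatment interruptions do not trigger withdrawal.

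**Duration.** Section 7.2.4 states "Participants will be followed for ≥ 2 years" and "The duration of the registry-based study is approximately 5 years". It gives the reason for the enrolment window: "Enrolment will close 3 years after the start of the study to ensure participants are followed for" at least 2 years. The same section lists the 180-day limit among the stopping reasons. Section 7.1 is worded more carefully: at least 2 years, or until one of those reasons occurs.

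**The concern.** The endpoints describe what happens to a participant after starting odevixibat. The collection rule describes what happens while the participant is on odevixibat and for about six months after. These are different quantities, and the protocol reports the second under the name of the first.

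The gap probably does not fall at random. Section 5.2 says that diversion is used for intractable pruritus, and Section 5.3 gives cholestatic pruritus as the authorised use of odevixibat. Section 7.2.9 allows discontinuation after adverse events or Special Situations, which by Section 9.1.3 include lack of effectiveness. A participant who stops because the drug failed is a natural candidate for a primary event. Kaplan-Meier assumes that people censored at a given time carry the same later risk as those still followed. Section 7.9 does not list this among the limitations.

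At stake is the primary objective, the incidence of diversion, transplant and all-cause death. With 30 to 45 participants, a few unrecorded events change the result visibly.

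**Working it through.** **1. The plan's own figure.** Study duration minus enrolment window: 5 − 3 = 2 years. The 2-year minimum reproduces as an administrative minimum.

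**2. What the 180-day rule does to it.** Follow-up is shorter than 2 years for anyone whose last dose falls before day 730 − 180 = 550 after enrolment, about month 18. At a constant stopping rate *d* per year, the share is 1 − exp(−*d* × 550/365.25). That gives 14% for *d* = 0.10 and 26% for *d* = 0.20 (both rates assumed).

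**3. Events missed and Kaplan-Meier error.** The protocol gives neither a stopping rate nor an off-drug event rate. Assumptions:
- event hazard on drug *h* = 0.03 to 0.05 per year
- stopping rate *d* = 0.10 to 0.20 per year
- hazard after stopping *h₂* = *h* × 1, 2, 3 or 5
- administrative follow-up uniform over 2 to 5 years (3-year enrolment, 5-year study)
- treatment starting at enrolment
- censoring at last dose plus *c* = 180/365.25 = 0.4928 years

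Event-free probability with complete follow-up:

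S(t) = exp(−(h+d)t) + ∫₀ᵗ d·exp(−(h+d)s)·exp(−h₂(t−s)) ds

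The planned Kaplan-Meier curve instead follows the average hazard among those on drug or within *c* of stopping.

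Worked case: h = 0.05, d = 0.20, ratio 5. Here h₂ = h + d = 0.25, so the integrals are simple.
- True value: S(3) = exp(−0.75) × (1 + 0.2 × 3) = 0.4724 × 1.6 = 0.756.
- Cumulative hazard seen up to *c*: 0.25c − ln(1 + 0.2c) = 0.1232 − 0.0940 = 0.0292.
- Hazard seen after *c*: (0.05 + 0.25 × 0.0986)/(1 + 0.0986) = 0.0679 per year. Over 3 − 0.4928 = 2.507 years this adds 0.1703.
- Planned curve at 3 years: exp(−0.1995) = 0.819. Overstatement: 0.819 − 0.756 = 6.3 points.

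All scenarios. Each cell shows the share of events in the study window that is missed, then the overstatement of 3-year event-free survival in percentage points:

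| h, d | ratio 1 | ratio 2 | ratio 3 | ratio 5 |
|---|---|---|---|---|
| 0.03, 0.10 | 12%, 0 | 20%, 0.7 | 26%, 1.4 | 33%, 2.6 |
| 0.03, 0.20 | 22%, 0 | 33%, 1.3 | 40%, 2.4 | 47%, 4.5 |
| 0.05, 0.10 | 12%, 0 | 19%, 1.1 | 24%, 2.1 | 30%, 3.6 |
| 0.05, 0.20 | 22%, 0 | 32%, 2.0 | 38%, 3.6 | 43%, 6.3 |

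In counts, for 45 participants with h = 0.03, d = 0.20 and ratio 3, about 6.7 events occur in the window and 4.1 are recorded.

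**4. Reading the table.** The ratio 1 column separates two effects. Stopping collection always loses events, so a crude proportion is too low. It biases Kaplan-Meier only if risk changes after stopping.

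**The case against.** **The limit was deliberate.** The objective and the first endpoint speak of chronically treated participants, and Appendix 1 records the extension to 180 days as an FDA request. On treatment plus a tail is a coherent target. This stands as far as it goes: relabelling the endpoints would also remove the contradiction. But the survival definitions do not state that target, and the amendment rationale does not say that 180 days suffices for them.

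**The size is assumed.** This stands. A reader might take it as shown that the survival curves are biased. The documents support only that the bias is plausible, and at an unchanged hazard it is zero. The top of the range is also extreme: in the worked case about 42% have an event by 4.9 years, whereas Section 5.2 puts transplant at 15% to 25% during childhood (for a narrower outcome).

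**Imprecision dominates.** Near 82% event-free, ignoring censoring, the 95% half-width is 1.96 × √(0.82 × 0.18/n), or 14 points at n = 30 and 11 at n = 45. That exceeds the largest 3-year bias above. But the interval would be centred in the wrong place, and wide intervals do not restore lost events.

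**Two years is already qualified.** A reader might infer that a firm 2-year promise is broken. Section 7.1 qualifies it, and Section 7.2.4 lists the stopping reasons beside it. What remains is an unconditional sentence that needs editing.

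**Deaths after transplant.** Section 5.2 says "The 5-year survival post-transplant in this population is about 80"%, and a reader might infer that most deaths after transplant go unseen. The documents do not support this. Nothing says that odevixibat stops at transplant. Prior transplant is an exclusion and the study lasts about 5 years, so a 5-year post-transplant horizon does not apply. For transplant-free survival, transplant is itself the event.

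**Conclusion.** The point holds. Followed exactly, the protocol fails to record primary events that occur more than 180 days after the last dose, although its endpoint definitions include them. Crude incidence is understated whenever such events occur. Kaplan-Meier estimates, including overall survival, are too favourable if those who stop have a higher later risk.

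Under the assumed rates, 12-22% of events are missed with no Kaplan-Meier bias at an unchanged hazard. At hazard ratios of 2 to 5, about 19-47% are missed, with a 3-year overstatement of about 0.7 to 6.3 points. The direction of the incidence error follows from the text. All the sizes rest on assumptions.

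Two related points are minor:
- The last enrollee may have 18 to 24 months rather than 24. Follow-up ends at a routine visit (Section 7.2.7: "The End of Study for participants will be the last Follow-up Visit as per routine clinical practice performed before the planned end of data collection"), and visits are expected at least every 6 months.
- Withdrawal applies if "They enroll in any interventional clinical trial" (Section 7.2.8), which is broader than the exclusion "Currently participating in any interventional clinical trial for ALGS" (Section 7.2.2).

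**What to change.** - Keep the 180-day limit for adverse events, laboratory values and growth.
- For every participant who has not withdrawn consent, record the dates of biliary diversion, liver transplant and death (or the date last known alive) to the end of data collection, whether or not odevixibat continues. Chart review or caregiver contact is enough; no extra test or visit is needed. Amend the withdrawal rule in Section 7.2.8 to allow this.
- Report the primary endpoints on these data. Show the curve censored at last dose plus 180 days as a sensitivity analysis.
- If the sponsor declines, relabel the primary endpoints as on treatment plus 180 days, qualify overall survival in the same way, and add the limitation to Section 7.9.
- Either way, reword the unconditional 2-year sentence in Section 7.2.4 to match Section 7.1.

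**Cost:** a protocol and consent amendment, a few eCRF fields, and a periodic status check for 30 to 45 people. The caregiver contacts that the protocol now encourages serve attendance at routine visits, so tracing people who have stopped is new work. Some who leave the site will be lost. The change should come early, because events after withdrawal may not be recoverable later.

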7.2.10 Early Study Termination

The sponsor can decide at any time to discontinue this registry-based study for any reason. Investigators will be informed of the decision. Independent Ethics Committees (IECs)/Institutional Review Boards (IRBs) and Competent Authorities (CAs) will also be informed if required by local regulations.

7.3 **Endpoints and Variables**

7.3.1 **Endpoints**

7.3.1.1 Primary Endpoints

- Incidence of biliary diversion surgery, liver transplantation, or death in participants with ALGS chronically treated with odevixibat.
- Surgical biliary diversion-free survival, defined as time from the start of odevixibat treatment to the first occurrence of surgical biliary diversion or death.
- Liver transplant-free survival, defined as time from the start of odevixibat treatment to the first occurrence of liver transplant or death.
- Overall survival, defined as time from the start of odevixibat treatment to death.

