7.7.2.1 Evaluation of Primary Endpoint

The incidence of biliary diversion surgery, liver transplantation, or death will be assessed using descriptive statistics. Depending on the data available, event free survival endpoints will be summarized using the Kaplan-Meier method. Median time to event with 2-sided 95% CIs and the first and third quartiles will be reported. Survival curves will be presented as well. In addition, survival probability estimates at 6 months, 12 months, and then every 6 months and the associated 2-sided 95% CIs will be reported.

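### The three-outcome primary endpoint has no time-to-event form, and diversion-free survival does not count liver transplant as an event

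*Protocol*

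**What the plan says.** The primary objective (Section 6.2.1) names three outcomes: diversion surgery, transplantation and death from any cause. Section 7.3.1.1 then sets four primary endpoints. The one listed first is the composite, given as an incidence with no time origin: "Incidence of biliary diversion surgery, liver transplantation, or death in participants with ALGS chronically treated with odevixibat". The next is a survival endpoint with two of the three outcomes as events: "Surgical biliary diversion-free survival, defined as time from the start of odevixibat treatment to the first occurrence of surgical biliary diversion or death". The remaining two share that time origin: transplant-free survival ends at whichever of transplant and death comes first, and overall survival ends at death alone.

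The analysis section treats them in two ways. The composite gets a plain summary: "The incidence of biliary diversion surgery, liver transplantation, or death will be assessed using descriptive statistics". The survival endpoints get curves, with a proviso: "Depending on the data available, event free survival endpoints will be summarized using the Kaplan-Meier method". Section 7.7.2 summarizes categorical variables by frequencies and percentages.

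On background rates, Section 5.2 puts a figure on transplant: "Approximately 15% to 25% of patients with ALGS will require a liver transplant during childhood". For diversion it gives no rate and says only: "Biliary diversion surgery is occasionally used to treat intractable pruritus with some success".

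**The concern.** The composite is the only endpoint that matches the whole primary objective, yet it alone has no time origin and no time to first event. A percentage with an event mixes participants watched for very different periods. Kaplan-Meier, which handles this, is planned only for the narrower endpoints.

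The diversion-free curve has a related weakness. Transplant is not an event in it, so transplanted participants without diversion or observed death are treated either as still at ordinary risk (censored) or as doing well (kept event-free). Neither describes what happened to them. Read alone, the curve says nothing about transplant, and it stays level or rises slightly as transplants become more frequent. A reader who wants the chance of remaining alive without either operation cannot obtain it from any planned curve.

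**Working it through.** The protocol states no figure for this point, so there is nothing to reproduce. The check has three parts.

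**1. Which outcomes each primary endpoint counts (Section 7.3.1.1)**

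| Endpoint | Diversion | Transplant | Death | Form |
|---|---|---|---|---|
| Composite | yes | yes | yes | incidence |
| Diversion-free survival | yes | no | yes | time to event |
| Transplant-free survival | no | yes | yes | time to event |
| Overall survival | no | no | yes | time to event |

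No time-to-event row has all three.

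**2. Size of the omission in the diversion-free curve**

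Inputs:
- Transplant: 15% to 25% during childhood (Section 5.2), spread at a constant hazard over an assumed 18 years: −ln(0.85)/18 = 0.0090 and −ln(0.75)/18 = 0.0160 a year.
- Diversion 0.02 and death 0.01 a year: assumed, not in the protocol.
- Horizon: three years, assumed.

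Three-year failure:
- Transplant censored: 1 − exp(−0.03 × 3) = 8.6%, whatever the transplant hazard.
- Transplant kept as event-free (no diversion and, for simplicity, no death after it): 0.03/(0.03 + h) × [1 − exp(−(0.03 + h) × 3)], where h is the transplant hazard. This gives 8.5% at h = 0.0090 and 8.4% at h = 0.0160.
- Any of the three: 1 − exp(−0.0390 × 3) = 11.0%, and 1 − exp(−0.0460 × 3) = 12.9%.

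The gap between censoring transplant and counting it is 2.4 to 4.3 points. With 30 to 45 participants (Section 7.5) that is 30 × 0.024 = 0.7 to 45 × 0.043 = 1.9, or about one to two people.

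As an upper illustration, suppose the whole childhood risk fell within the three years. Failure from any of the three would then be 1 − 0.914 × 0.85 = 22.3% or 1 − 0.914 × 0.75 = 31.5%, where 0.914 = exp(−0.09).

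**3. Why a crude incidence is a weak summary here**

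Enrolment closes three years into a study of about five (Section 7.2.4), so participants who stay on treatment are followed for roughly two to five years after enrolment. Those who stop leave within 180 days of the last dose (Section 7.2.9). Participants already on odevixibat may join (Section 7.1). With the hazards above, the chance of any of the three events is:

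- over two years: 1 − exp(−0.0390 × 2) = 7.5% to 1 − exp(−0.0460 × 2) = 8.8%;
- over five years: 1 − exp(−0.0390 × 5) = 17.7% to 1 − exp(−0.0460 × 5) = 20.5%.

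The same underlying risk therefore gives percentages that differ more than twofold, according to how long participants happen to be observed.

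**The case against.** The strongest reply is that each surgical outcome has its own endpoint, named for what it measures. If participants were being transplanted, transplant-free survival, a primary endpoint reported alongside, would fall. This stands. A reader might infer that the plan hides transplants or scores every transplanted participant as a success. The documents do not support that: transplants count in two of the four primary endpoints, and a diversion before transplant or an observed death after it is an event in the diversion-free curve too.

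Nor should transplant simply be made an event in diversion-free survival. That would turn it into the three-outcome composite and lose the diversion-specific information.

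A reader might also infer a much larger effect by assuming transplant hazards of 2, 5 or 8% a year, which give three-year failure from any of the three of 13.9%, 21.3% and 28.1%. Over 18 years those hazards imply about 30%, 59% and 76% transplanted, all above the protocol's range. A higher risk in treated patients is possible, but the protocol gives no figure for it. Nor can transplant be ranked numerically above diversion, since no diversion rate is given.

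Finally, the choice between censoring and retaining transplanted participants belongs to the SAP, as does a possible person-time rate for the composite. That is fair, and the absence of such detail is no fault. But neither choice makes transplant an event under the protocol's definition, and a rate would not supply the missing time to first event. Endpoint definitions are the protocol's to set.

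**Conclusion.** The point holds as a gap in the set of primary endpoints. The composite that matches the objective is limited to a descriptive incidence under very unequal follow-up, and no time-to-event endpoint covers all three outcomes. Diversion-free survival is correctly named but cannot be read as freedom from surgery.

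Anchored to the protocol's childhood transplant figure, the difference at three years is about 2.4 to 4.3 percentage points, and more if treated patients have a higher transplant risk. This rests on constant, independent hazards, an assumed 18-year spread, and assumed diversion and death rates. Treating transplant as a competing event further presumes that diversion is unlikely after it; the protocol does not say so, although Section 5.2 reports improved liver parameters in about 90% after transplant.

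No formal testing is planned (Section 7.9), so no error rate or sample size is affected. The change is worth making, but the gap does not invalidate the study.

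**What to change.** 1. Add event-free survival to Section 7.3.1.1: time from the start of odevixibat to the first of biliary diversion, liver transplant or death. In Section 7.7.2.1, analyse it by Kaplan-Meier as the time-to-event form of the first-listed primary endpoint, with the quartiles and six-monthly estimates already planned for the other curves.
2. Supplement the diversion-free curve with a cumulative incidence function (Aalen-Johansen) for diversion, with transplant and death as competing events.
3. Keep the four existing primary endpoints as they are.

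The cost is a wording change and limited extra analysis. Surgery dates, death dates and the odevixibat start date are already collected (Sections 7.3.2.4, 7.3.2.6 and 7.3.2.8), so no new data or participant burden arise. The drawback for the sponsor is that the added curve will look less favourable than the diversion-free curve.
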